The study is designed to assess the safety and potential benefit of the C-Pulse® System before initiating a wider randomized clinical trial to demonstrate safety and effectiveness. The effect of the C-Pulse® system in relieving heart failure symptoms in patients with ACC/AHA Stage C, NYHA Class III-ambulatory Class IV heart failure will be documented with this study.

This Feasibility Study is multi-center study which is being expanded to include up to 9 centers in the US and potentially some OUS centers. The study population will be expanded to include 40 patients enrolled and implanted with the C-Pulse® System. The period of follow-up for the initial 20 patients will be 6 months to assess the safety and performance before initiating the pivotal clinical trial. It is desired that the system be used all the time. However, the System should not be “Off” for greater than one hour at any one time for a maximum of four hours total per day during the study period. For the extent of the trial period (6 months), C-Pulse® should be used at least 20 hours per day (i.e. device must be used greater than 80% of the time). The patient must limit the duration of disconnection to 15 minute intervals for a maximum of 4 hours total during the trial period to ensure the device is used for 80% of the time. The Driver logs patient usage automatically and stores into the system files.

Patients will be followed for up to 10 years or until the study is closed.

If a patient undergoes anesthesia for the purpose of C-Pulse implantation but does not receive a C-Pulse System, the patient will be followed until 30 days or discharge whichever occurs first.

[figure not shown]

Figure 1A. Study Design

Patients will be enrolled into the trial upon providing informed consent. Procedures related directly to the study must not be performed prior to informed consent. Data collection will be noted prior to implantation of the device and at one, three, and six months following implant and then long term at 12 and 18 months followed by annually post-implant for five years. Adverse events will be collected throughout the study until study closure and will be adjudicated by the Clinical Event Committee (CEC).

Progress reports of the clinical outcomes will be reviewed by the DSMB after enrollment of five (5) patients and twice per year thereafter, unless slow enrollment does not warrant this meeting frequency.

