- Inadequate device tracking or off-label investigator device use
- Failure to follow-up patients per scheduled follow-ups
- Failure to submit data in a timely manner
- Failure to follow-up with findings on a monitoring report

Note that any patients previously enrolled will continue to be followed at this institution by the investigator or a named co-investigator.

Laboratory Accreditation and Normal Values

Before initiation of the study, appropriate accreditation for all laboratories to be used in the study must be provided to the sponsor. Throughout the study, the Investigator must provide documentation of all renewals of accreditation. The ranges of values considered normal for the laboratory tests being performed for the study must be provided to Sponsor in order to facilitate pooling of the data.

PROCEDURES

Screening and Patient Informed Consent

Prior to enrolling patients, each investigational center IRB will be required to approve the study Investigation Plan, and the Patient Informed Consent. In addition, patients will be required to provide written informed consent for enrollment. A Screening Log is located within the site Regulatory Binder and should be completed for all patients screened but not enrolled for the study.

Patients will undergo a pre-implant baseline assessment to ensure they meet the inclusion and exclusion criteria no more than **30 Days** prior to the implant date. Patient informed consent must be signed prior to conducting any screening or baseline testing procedure performed for study purposes. **When a patient signs an informed consent for the study, he/she is considered enrolled in the study and will be assigned a study identification number by the center.** To minimize the burden to the patient, data collected as standard of care and not for the specific reason for assessing study eligibility may be used for baseline data points as outlined in the informed consent. These tests will suffice for the respective portion of the baseline dataset if collected within the pre-implant evaluation timeframe of 30 days prior to implant. Upon completion of screening, all patients that do not satisfy the eligibility criteria will be promptly study exited without proceeding to implantation. Study Exit of these patients must be documented on the Study Exit Form. Any patient whom undergoes anesthesia for the purpose of C-Pulse implantation but does not receive the device will be monitored for adverse events as

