This feasibility study intends to examine the effect of C-Pulse® on long-term heart failure, and to look for trends in performance indicators. This study is not powered to detect statistical significance. As such, clinical judgment is required to assess device safety and potential efficacy from data collected during this study. This clinical judgment will be provided by the DSMB.

Justification of Methodology

This study is designed as an open-label single-arm study to develop a further understanding of the C-Pulse®. It will provide safety and efficacy information for patients in whom C-Pulse® is implanted and maintain counterpulsation for six months or longer.

At six months post-procedure, the patients will provide an adverse event profile related to surgical placement of the C-Pulse® and six months employment of C-Pulse® counterpulsation. After six months of the study there will be additional information related to the adverse event profile. The patients will provide an adverse event profile for patients in whom C-Pulse® is placed and maintain counterpulsation for greater than six months.

Similarly, these patients will provide an efficacy profile. At six months post-procedure, the patients will provide information on how well a patient improves since baseline through six months of counterpulsation. After six months these patients provide additional efficacy information related to how well a patient improves since baseline through greater than six months of counterpulsation.

Primary Safety Measures

The safety of the C-Pulse® will be evaluated by reviewing a composite of the device-related adverse events through six months, as classified by the CEC. The composite device-related adverse event rate will be the percent of patients who experience at least one of the following adverse events as adjudicated by the CEC as device-related out of the total number of patients:

- Death
- Neurological Dysfunction
- Aortic Disruption
- Myocardial Infarction
- Major Infection
- Any other device-related adverse event (as adjudicated by the CEC)

The definitions for these adverse events are provided in the Adverse Event Definitions section.

Performance Requirements

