Safety will be represented in the composite device-related adverse event rate which will be reported with its 95% two-sided exact confidence interval. The composite device-related adverse event rate will be assumed to follow the Binomial Distribution. The DSMB will decide the clinical acceptability of this observed event rate in assessing trial success.

Additionally each event will be presented with its respective rate and confidence interval. Death will be separated into deaths that occur before 30-days post-procedure and those that occur between 30-days post-procedure and 6 months.

Efficacy measurements

The efficacy of C-Pulse® will be evaluated by assessing the change of the efficacy variables from baseline to 6 months post-implant. The following measurements will be taken at baseline and 6-months.

- Peak VO₂
- Quality of Life as measured by the Minnesota Living with Heart Failure (MLWHF)
- HF Symptoms as measured by NYHA
- Six Minute Hall Walk Test

Performance Requirement

Trial success will be evaluated by analyzing each patient's response to the four efficacy variables. A responder analysis will be performed for each patient assessing the response to each of the four efficacy variables. Each efficacy variable will be assessed for clinical improvement ("responder"), decline ("non-responder") or no change ("indeterminant").

Clinical improvement will be defined for each efficacy variable as:

- 1.2 ml/kg/min improvement in peak VO₂
- 7 point improvement in MLWHF score
- 1 class improvement in NYHA
- 50 meter improvement in the Six Minute Hall Walk

Clinical decline will be defined for each efficacy variable as:

- 1.2 ml/kg/min decrease in peak VO₂
- 7 point decrease in MLWHF score
- 1 class decrease in NYHA
- 50 meter decrease in the Six Minute Hall Walk

A patient that shows no improvement or decline in a particular endpoint will be labeled as "indeterminate" for that endpoint.

The overall percentage of responders, non-responders and indeterminates for each efficacy variable along with the respective 95% two-sided exact confidence interval will be presented. Additionally the point estimate for the average change and its respective standard deviation will be presented for peak VO₂, MLWHF, and the Six Minute Hall Walk. The improvement in NYHA will be presented by a cross-tabulation summary. The DSMB will decide the clinical acceptability of this responder analysis in assessing trial success.

Secondary Objectives

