This is a single-arm study designed to determine the safety of the C-Pulse® as well as give an insight into the efficacy of counterpulsation.

Because estimates from this study will be used to power the pivotal study, this study must be able to provide such estimates. A sample size of 20 implanted patients is considered clinically sufficient to give indications of both safety and potential efficacy. With this sample size, we feel we can decide whether to proceed to a pivotal study, determine endpoints for such a study, and design the study to answer the proposed hypotheses. Up to approximately 10 additional subjects may be enrolled to account for subjects who do not meet inclusion/exclusion criteria involving non-standard clinical practices.

Subjects for Analysis

Patients will be included in two analyses. The primary analysis will be an “as- treated” analysis, wherein only subjects in whom the device is placed are analyzed. The secondary analysis will be an “intention to treat” analysis, wherein all followed-up subjects will be analyzed.

RISK ANALYSIS

SHC has evaluated the potential risks and benefits (listed below) associated with the C-Pulse® and its appropriateness for therapy for symptomatic Stage C HF patients with NYHA Class III–ambulatory Class IV symptoms. Evaluation is based on the preclinical and clinical experiences to date. The adverse event definitions in the previous sections highlight and expose a standard level of expected risks. Any unanticipated risks and associated events will be captured through the adverse event reporting.

Potential Risks

Risks Related to the Implantation Procedure

Surgical risks along with mitigations specific to the C-Pulse® system include:

- Damage to Cuff on implantation not detected
- Misplacement of ECG lead – not able to sense ‘R’ wave appropriately

Implantation is an invasive procedure requiring a median sternotomy and the use of general anesthesia and mechanical respiratory support. The potential risks associated with the implant procedure also include those associated with any cardiothoracic surgery, including implantation of devices and include the following:

- Bleeding
- Infection
- Neurological Dysfunction
- Renal Dysfunction
- Cardiac Arrhythmias
- Pericardial Fluid Collection
- Aortic disruption
- Device Malfunction
- Hemolysis
- Hepatic Dysfunction
- Hypertension
- Myocardial Infarction
- Psychiatric Episode
- Respiratory Failure
- Right Heart Failure
- Arterial Non–CNS Thromboembolism

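### Patients anesthetized for C-Pulse implantation but not implanted are outside the primary analysis set, the set labelled intention to treat depends on an undefined follow-up status, and 30-day deaths after a failed attempt can be missed

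*Combined protocol and SAP*

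**What the plan says.** The section Subjects for Analysis names two sets. The primary analysis is as-treated, "wherein only subjects in whom the device is placed are analyzed". The secondary analysis is called intention to treat, "wherein all followed-up subjects will be analyzed". Enrollment itself is defined elsewhere (Study Size and Duration; Screening and Patient Informed Consent) as the signing of consent.

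Under Primary Safety Measures, the main safety quantity is a "composite of the device-related adverse events through six months, as classified by the CEC". Its rate is the share of patients with at least one event "adjudicated by the CEC as device-related out of the total number of patients". Neither analysis set is named there. Under Performance Requirements the rate is to be "reported with its 95% two-sided exact confidence interval", and the same section adds: "Death will be separated into deaths that occur before 30-days post-procedure", with later deaths up to 6 months shown separately.

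Failed implant attempts have their own rule. Screening and Patient Informed Consent says that any patient who "undergoes anesthesia for the purpose of C-Pulse implantation but does not receive the device will be monitored for adverse events". The Design section gives the duration: "the patient will be followed until 30 days or discharge whichever occurs first".

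**The concern.** An intention-to-treat set is fixed by a decision made before outcomes are seen. A set that requires follow-up is fixed by something that happens after enrollment, so the label is wrong. Without a definition (any contact, 30 days or 6 months), two analysts could build different sets from the same data.

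Failed attempts are foreseeable. The protocol writes a rule for them. It also schedules an epi-aortic ultrasound and an aortic circumference measurement during the operation, and either might stop an implant after surgical exposure has begun. The Risk Analysis lists bleeding, neurological dysfunction, aortic disruption and death among the risks of the procedure. A primary analysis restricted to implanted patients cannot show any of this harm in a patient whose implant was abandoned.

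Safety is the stated primary endpoint of this feasibility study. The DSMB judges acceptability clinically, with no numerical threshold, and the estimates feed the pivotal design. The DSMB needs to know whom each rate describes.

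**Working it through.** **Step 1. Who is in which set, reading the definitions literally.**

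| Patient | As-treated (primary) | Followed-up (secondary) |
|---|---|---|
| Implanted, followed | In | In |
| Implanted, later lost | In | Unclear: followed-up is undefined |
| Anesthetized, not implanted | Out | In, on the natural reading, since monitoring is mandated |
| Consented, exited at screening | Out | Out, on the natural reading; no exposure to the implant procedure |

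**Step 2. The 30-day death.** Required follow-up after a failed attempt ends at min(discharge, day 30). If discharge is on day d < 30, a death between day d and day 30 lies outside required follow-up. Membership of the secondary set does not cure this, because the information is not collected.

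**Step 3. Size.** The plan states no expected event rate or precision target, so there is no figure to reproduce. Inputs from the documents are n = 40 implanted (Study Size and Duration, after expansion), n = 20 (Sample Size Determination) and the exact two-sided 95% binomial interval. Assumed inputs are x events among the implanted, k failed attempts, and e of those k with a counted event.

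- As-treated rate: x/n. All-attempted rate: (x + e)/(n + k).
- The rate rises when e/k > x/n and falls when e/k < x/n.
- Interval: lower limit is the 2.5% quantile of Beta(x, n − x + 1); upper limit is the 97.5% quantile of Beta(x + 1, n − x), using the relevant count and denominator.

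| n, x | As-treated | k | All attempted, e = 0 | All attempted, e = k |
|---|---|---|---|---|
| 40, 2 | 5.0% (0.6–16.9) | 1 | 2/41 = 4.9% (0.6–16.5) | 3/41 = 7.3% (1.5–19.9) |
| 40, 2 | 5.0% (0.6–16.9) | 2 | 2/42 = 4.8% (0.6–16.2) | 4/42 = 9.5% (2.7–22.6) |
| 40, 2 | 5.0% (0.6–16.9) | 4 | 2/44 = 4.5% (0.6–15.5) | 6/44 = 13.6% (5.2–27.4) |
| 40, 0 | 0% (0–8.8) | 2 | 0/42 = 0% (0–8.4) | 2/42 = 4.8% (0.6–16.2) |
| 20, 2 | 10.0% (1.2–31.7) | 2 | 2/22 = 9.1% (1.1–29.2) | 4/22 = 18.2% (5.2–40.3) |

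Between these extremes, one event in two failed attempts at n = 40, x = 2 gives 3/42 = 7.1%.

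**Step 4. Implanted patients lost to follow-up.** Take 2 events in 40 implanted patients, with 2 others lost. Dropping the lost patients gives 2/38 = 5.3% (0.6–17.7). Keeping them as non-events gives 2/40 = 5.0% (0.6–16.9). Counting both as events gives 4/40 = 10.0% (2.8–23.7). The statistical section gives no rule for choosing among these.

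**Step 5. Which outputs the change affects.** The composite counts only events that the CEC adjudicates as device-related. Adverse Event Classification makes an event procedure-related when it results directly from implantation and cannot be attributed to a device or implant tool. The e = k column therefore applies to the composite only if those events are adjudicated device-related. If they are all procedure-related, the e = 0 column applies. The 30-day death split and the per-event and procedure-related rates (Secondary Objectives, statistical section) do not have that restriction. They are where an all-attempted denominator matters most.

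**The case against.** A reader might infer that failed attempts and unfollowed patients disappear from every safety denominator. The documents do not support that. Failed attempts have mandated adverse event monitoring and so plausibly sit in the secondary set. Implanted patients who are later lost remain in the as-treated set. Those who leave both are mainly consented patients exited before surgery. On its natural reading, the secondary set is already close to an all-attempted set.

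A reader might also infer that the safety profile must look too favorable. That does not follow either. Event-free failed attempts would lower the rate, and with the composite limited to device-related events, enlarging its denominator alone could make it look better. Nor is it established that the secondary set selects on outcome: a patient who dies in hospital under the mandated monitoring has been followed.

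Finally, events in failed attempts are collected, the CEC reviews all adverse events and deaths, and the DSMB sees study data beyond a single rate. The study claims no power and relies on clinical judgment.

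All of this stands, and it limits the point to what the table in step 1 shows. It does not remove the exclusion from the primary set, the mislabelled and undefined secondary set, the unnamed composite denominator, or the gap between discharge and day 30. Nor is the device-related restriction absolute. The definition covers harm from the presence or operation of the device, so injury from a cuff that was tried and removed could count.

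**Conclusion.** The point holds in this limited form. The primary set leaves out surgically exposed patients, the intention-to-treat label does not fit a set conditioned on an undefined later status, and a post-discharge death before day 30 after a failed attempt can go unrecorded. The rates put to the DSMB can be too low if failed attempts carry more harm than implanted patients do, or slightly too high if they carry none.

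The size is unknown. The documents give no number of failed attempts and no event rates, so every count above is an assumption. With 2 events in 40 and one to four failed attempts, the all-attempted rate ranges from 4.5% to 13.6%, against 5.0% as-treated. For the composite, the upper figure also requires every added event to be adjudicated device-related. No figure stated in the plan is contradicted. This is a cheap improvement.

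**What to change.** - Define a safety set: every patient in whom anesthesia for C-Pulse implantation was begun, whether or not implanted or later followed.
- Use it as the denominator for 30-day death and for the all-event, serious and procedure-related adverse event rates.
- Report the device-related composite on this set beside the implanted set, and name the set behind each denominator. Failed attempts are observed for at most 30 days, so note that their six-month status is incomplete.
- Keep the implanted set for efficacy.
- Drop the intention-to-treat label, or redefine it as all attempted. If followed-up is kept anywhere, define it.
- State how patients without complete six-month safety follow-up are counted.
- Record vital status at day 30 for patients attempted but not implanted.

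The cost is a few sentences in the statistical section and a status check in what should be a few patients. Reported rates may shift slightly in either direction.

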APPENDIX A: ABBREVIATIONS AND ACRONYMS

CEC	Clinical Events Committee
MAB	Medical Advisory Board
AE	Adverse Events
DSMB	Data Safety and Monitoring Board
HF	Heart Failure
ECG	Electrocardiogram
BTT	Bridge to transplant
VAD	Ventricular Assist Device
TTE	Transthoracic echocardiography
FDA	Food and Drug Administration
TEE	Transesophageal echocardiography
CRT	Cardiac Resynchronization Therapy
NYHA	New York Heart Association
QOL	Quality of Life
LVAD	Left Ventricular Assist Device
DT	Destination Therapy
IAB	Intra Aortic Balloon
IDE	Investigational Device Exemption
ICP	Implantable Counterpulsation Pump
PIL	Percutaneous Interface Lead
IR	Infra-red
CPX	Cardiopulmonary Exercise Testing
IRB	Investigational Review Board
MLWHF	Minnesota Living With Heart Failure
KCCQ	Kansas City Cardiac Quality of Life Questionnaire
CXR	Chest Xray
ECHO	Echocardiogram
eCRF	Electronic Case Report Form Template
ICU	Intensive Care Unit
IV	Intra-venous
PRBC	Packed Red Blood Cells

APPENDIX E: SUMMARY OF PREVIOUS STUDIES

Experience to date by Sunshine Heart provides evidence of safety and performance. These include:

INTRA–OPERATIVE CLINICAL FEASIBILITY STUDY

The aim of this study was to determine the safety and performance of a new method of non blood contacting counterpulsation utilizing an inflatable cuff (C-Pulse) around the ascending aorta.

In 6 patients undergoing first time off pump coronary bypass surgery via sternotomy, the C-Pulse was secured around the ascending aorta and attached to a standard counterpulsation console. At baseline, and with 1:2 and 1:1 augmentation, hemodynamic and echocardiographic parameters of ventricular function and coronary flow were measured. High intensity transient signals (HITS) were measured using transcutaneous Doppler over the right common carotid artery.

No complications occurred.

With C-Pulse there was no significant change in heart rate and blood pressure, and no increase in HITS. There was a 67% increase in diastolic coronary blood flow (mean left main diastolic velocity time integral 15.3 cm unassisted vs 25.1 cm assisted, $p < 0.05$). Measurements with transesophageal echocardiography, at baseline and with 1:1 counterpulsation, demonstrated a 6% reduction in end diastolic area ($p = \text{NS}$), 16% reduction in end systolic area ($p < 0.01$), 31% reduction in LV wall stress ($p < 0.05$), and a 13 % improvement in fractional area change ($p < 0.005$). It was concluded that C-Pulse counterpulsation augments coronary flow and reduces left ventricular afterload.

LONG–TERM EXTRA–AORTIC BALLOON COUNTERPULSATION IN SHEEP

This study was undertaken to examine the effect of chronic counterpulsation with C-Pulse on the integrity of the ascending aorta in sheep at 5 and 10 months.

A pre-shaped cuff, consisting of a polyurethane balloon and polyester wrap, was implanted around the ascending aorta via a left mini-thoracotomy in 11 adult sheep. An endocardial ECG sensing lead was implanted via the right external jugular vein. The balloon's gas line and the sensing lead were brought out percutaneously over the back and connected to a Datascope 90 IABP console.

Sheep were counterpulsated for approximately five and ten months. Prior to post-mortem, intra-aortic ultrasound examination was completed to examine balloon function.

Following euthanasia, an autopsy was conducted in all sheep; particular attention was paid to the heart, brain and kidneys. Detailed histology was completed on the heart and great vessels with the attached device, from each sheep.

Intra-aortic ultrasound showed each cuff to be inflating and deflating in a normal pattern following 5 and 10 months operation. Sheep were terminated at five months (6) and 10 months (5).

One sheep was euthanized at 5 months because it became ill over several days; at autopsy it was found to have a bacterial infection involving the cuff and the aorta resulting in a contained aortic rupture. In two other sheep (at 5 and 10 months, respectively) non-disruptive aortitis was noted at post-mortem and this was confirmed by microscopic pathology.

Hence the thoracic aorta was assessed microscopically in 8 sheep; 4 at 5 months and 4 at 10 months. Histology of the aortic wall at the root and arch appeared normal. Sections through the mid-ascending aortas revealed the peri-aortic implants were well incorporated by the adventitial peri-aortic tissues and that there was no disruption to the endothelial surfaces. Histology demonstrated that for each of the 8 sheep the intima and inner half of the media, measuring 0.6–0.9 mm thick, appeared normal. Findings in the outer one third to one half of the aortic wall included muscular atrophy, thin-walled blood vessels, petechial haemorrhages, small focal strips of coagulative necrosis (0.1–0.3 mm thick) and viable reparative tissue responses. Those at 10 months, displayed a recognizable reparative microvascular (arterial and venular) pattern with less necrosis than at 5 months. The changes were circumferential. While the cuffed aortic wall was thinner than the normal wall, there was no evidence of progressive damage to the inner media and intima when comparing results from sheep at 5 months to those at 10 months.

